## 4.3 Rationale

Although the properties of the ideal local hemostatic agent may vary according to the surgical specialty, some properties are universally valued including: rapid and effective control/cessation of bleeding; ability to make effective contact with the bleeding surface; acceptable safety profile; and ease of preparation and use.

According to Spotnitz *et al.*, the ideal hemostat, sealant or adhesive must have certain performance characteristics (safety, efficacy, usability, cost, and approvability) that enable it to be used by surgeons. Biom'up has developed and manufactured a hemostatic device, HEMOBLASTTM, which is ready to use without any preparation required. This post-market study will be conducted to assess time to hemostasis, which includes the time of device preparation.

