## 6.4.1 Intraoperative Inclusion Criteria

A subject must then meet all of the following intraoperative inclusion criteria:

- Subject does not have an active or suspected infection at the surgical site;
- Subject in whom the Investigator is able to identify a TBS for which any applicable conventional means for hemostasis are ineffective or impractical; and
- Subject has a TBS with minimal, mild, or moderate bleeding.1

If all of these intraoperative eligibility criteria are met, then the subject is formally enrolled into the clinical study and randomized. Each subject will have one TBS assessed and documented for the purposes of this study.

The bleeding severity of the TBS will be assessed via the SBSS/SPOT GRADETM for intraoperative inclusion, which is immediately prior to enrollment. The bleeding severity of the TBS will also be assessed and confirmed immediately prior to hemostat application, as bleeding severity may change between the time of enrollment and when the hemostat is ready to be applied. Both bleeding severities will be recorded on the Intraoperative CRF. Both bleeding severities will be presented in the analysis of the study data.

If the bleeding severity at the time when the hemostat is ready to be applied is not minimal, mild, or moderate bleeding, then the TBS will not be treated. If another suitable TBS is identified, the subject may undergo intraoperative evaluations for that TBS. If another suitable TBS is not identified, the subject will be withdrawn from the clinical study.

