## 6.4.2 Randomization and Hemostat Application

Subjects will be randomized to receive HEMOBLAST™ or FLOSEAL in a 1:1 ratio:

- 52 subjects will be randomized to receive HEMOBLASTTM; and
- 52 subjects will be randomized to receive FLOSEAL.

To ensure balance through time, blocked randomization will be performed. Random block sizes of 2, 4, or 6 will be implemented to conceal treatment allocation. After enrollment and randomization, the assigned hemostat will be used in the subject.

A study-specific stopwatch will be used in the performance evaluations.

After randomization, the assigned hemostat will be opened and prepared. The study-specific stopwatch will be started at the time of hemostat outer packaging opening (time 00:00).

The assigned hemostat will be prepared and applied to the TBS per its respective Instructions for Use (IFU).

At time 03:00 (3 minutes after hemostat packaging opening), hemostasis will be assessed using the SPOT GRADETM. If the TBS is hemostatic (SPOT GRADETM score = 0), the performance evaluations are complete. If the TBS is not hemostatic (SPOT GRADETM score > 0), a re-application of the assigned hemostat will be performed per the respective IFU.

At time 05:00 (5 minutes after hemostat packaging opening), hemostasis will be assessed using the SPOT GRADETM. If the TBS is not hemostatic (SPOT GRADETM score > 0), the Investigator may use any means necessary to obtain hemostasis.

The study-specific stopwatch will run continuously until the 5 minute evaluation time point, except in cases where preparation of the hemostat is interrupted by other activities and obligations of the surgical staff. The study-specific stopwatch will be run by a trained and delegated study staff member. In cases where the individual(s) involved in preparing the hemostat are required to perform other activities, the stopwatch will be paused and restarted when preparation resumes. The number of interruptions will be recorded for each case.

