#### 6.4.5 Intraoperative Data Collection

The following data will be recorded on the Intraoperative CRF:

- Surgical procedure(s)
- Description of TBS
  - Location
  - Conventional means for hemostasis (pressure, suture, cautery, etc.)
- Confirmation of intraoperative eligibility criteria
- Approximate dimensions of target bleeding site
- SPOT GRADETM scores at baseline
  - Assessment of intraoperative eligibility
  - o Immediately prior to hemostatic device application
- SPOT GRADE™ score at 3 minutes
- SPOT GRADETM score at 5 minutes (if hemostasis is not achieved within 3 minutes)
- Randomization
  - Time of randomization
  - o Treatment arm
  - Device lot/batch number data
- Number of incidence(s) of interruption of hemostatic device preparation

- Satisfaction on time and ease of hemostatic device preparation
- Incidence of TBS re-bleeding prior to subject closure
- Incidence of any device deficiencies
- Incidence of any device-related adverse events

Table 7 below shows a timeline of intraoperative procedures.

Time Point (MM:SS)	Study Procedures or Assessments
Prior to 00:00	• Identify Target Bleeding Site (TBS)
	
 
Assign SPOT GRADE™ score
 

	Perform randomization
00:00 (start stopwatch)	
 
Open HEMOBLAST™ or FLOSEAL
 

	packaging and start preparation
0X:XX	• Assign SPOT GRADE ™ score immediately
	prior to hemostat application
03:00	
 
Assign SPOT GRADE™ score
 

	If SPOT GRADE TM score = $0$
	Intraoperative efficacy evaluation completed
	If SPOT GRADE TM score is NOT $0$
	
 
Re-apply HEMOBLASTTM or FLOSEAL
 

05:00	
 
Assign SPOT GRADE™ score
 

	If SPOT GRADE TM score = $0$
	Intraoperative efficacy evaluation completed
	If SPOT GRADE™ score is NOT 0
	Rescue treatment

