## 11.3.1.2 Methods of Analysis

The primary efficacy endpoint is the difference in the probability of TTH at 3 minutes comparing HEMOBLASTTM to FLOSEAL. Letting  $\theta$  denote the true difference in the probability of hemostasis at 3 minutes between HEMOBLASTTM to FLOSEAL, the trial will test the null hypothesis H0:  $\theta \le 0$  vs. the alternative hypothesis HA:  $\theta > 0$  using a one-sided level 0.025 Wald test. The resulting p-value based upon the asymptotic normal distribution and a corresponding (2-sided) 95% confidence interval for the difference in binomial proportions (HEMOBLASTTM minus FLOSEAL) will also be computed and reported.

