#### **11.3.3 Sample Size Justification**

The sample size for the proposed study is based on:

- Type I error  $\alpha = 0.025$  (one-sided);
- Type II error  $\beta = 0.10$ ;
- $\delta = 0.30;$
- $\theta_{\text{HEMOBLAST}^{\text{M}}} = 0.40 \text{ at } 3 \text{ minutes; and}$
- $\theta_{\text{FLOSEAL}} = 0.10 \text{ at } 3 \text{ minutes.}$

Based upon the above model specification, the proposed study will require approximately N=98 patients (49 patients per arm). While early discontinuation is expected to be rare, to account for potential loss of patients due to early discontinuation, a total of N=104 subjects (52 patients per arm) will be enrolled in order to ensure at least 90% power under the design assumptions while allowing for up to 5% attrition.

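### The 3-minute clock starts at package opening, a moment chosen after allocation is known, with no readiness condition, no time limit and no recorded opening time

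*Combined protocol and SAP*

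**What the plan says.** Section 6.4.2 states the start rule for both arms: "The study-specific stopwatch will be started at the time of hemostat outer packaging opening (time 00:00". The same section has the assigned device opened and prepared after randomization. Table 7 lists site identification, bleeding grade and randomization before 00:00, and opening at 00:00. Hemostasis is graded at 3 and 5 minutes on this clock, and the clock is paused when the people preparing the device are called to other duties. Only the number of interruptions is recorded.

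Among the Intraoperative CRF items in Section 6.4.5, "Time of randomization" is listed. The clock times of opening and of application are not.

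The devices differ in what follows opening. Section 4.3 describes HEMOBLAST as a device "which is ready to use without any preparation required", and Section 3.1 agrees. Section 3.3 says that FLOSEAL is supplied as a prep kit. Counting preparation time is deliberate (Sections 4.3 and 5.1.1).

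Section 6.4.1 requires a second grade just before application, because "bleeding severity may change between the time of enrollment and when the hemostat is ready to be applied". Both grades are recorded and presented. Section 11.1.4 makes 3-minute superiority the only criterion of study success.

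**The concern.** A timed endpoint is comparable between arms only if the clock starts at the same clinical moment in each. Here the start is an act of the treating team, carried out after the team knows which device it has. No masking of operator, timekeeper or assessor is described, no maximum interval from randomization to opening is written, and no readiness condition is set.

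The two devices give different reasons for choosing the moment. A device that needs no preparation can stay sealed until the surgeon is at a ready site, and then be opened and applied at once. A device that must be prepared gives a reason to open sooner and ready the site in parallel, with the clock running. Readying the site is not device preparation. Whether it counts should not depend on a choice made with knowledge of the arm.

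If the choice differed by arm, part of the observed 3-minute difference would come from the start rule and not from the devices. A sceptical reader could not be answered, because the interval cannot be reconstructed from the listed data.

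**Working it through.** **1. The plan's own figure.** Inputs from Section 11.3.3: one-sided alpha 0.025, power 0.90, HEMOBLAST 0.40, FLOSEAL 0.10, difference 0.30. The mean rate is 0.25.

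- Pooled formula without correction: n' = [1.960 × √(2 × 0.25 × 0.75) + 1.2816 × √(0.24 + 0.09)]² / 0.30² = 41.66.
- With continuity correction: n = (n'/4) × [1 + √(1 + 4/(n' × 0.30))]² = 48.10, so 49 per arm and N = 98. This matches.
- Attrition: 98 / 0.95 = 103.2, so 104. This matches.

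The timing issue does not touch this arithmetic.

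**2. What fixes and what records the start.**

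| Item | HEMOBLAST | FLOSEAL |
|---|---|---|
| Time 00:00 | package opening | package opening |
| Allocation known before 00:00 | yes | yes |
| Limit on randomization to opening | none written | none written |
| Readiness condition before opening | none written | none written |
| Clock time of opening on the CRF list | no | no |
| Work needed between opening and application | none | preparation |
| Clock paused if preparation is interrupted | little to interrupt | yes |

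The rule is symmetric. The incentive in choosing the moment is not.

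**3. What a one-arm shift would do.** The shift sizes are assumptions, because the documents give none. Other inputs: 52 per arm (Section 11.3.3) and the primary analysis of Section 11.3.1.2, "using a one-sided level 0.025 Wald test". Success is declared when (p1 − p2) / √[p1(1 − p1)/52 + p2(1 − p2)/52] exceeds 1.960. If the standard error is zero, success is declared when p1 exceeds p2. The probability is summed exactly over all pairs of binomial counts. The true rate without any timing effect is the same in both arms.

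| Shift in HEMOBLAST only | Common rate 10% (planned FLOSEAL rate) | Common rate 20% (assumed) |
|---|---|---|
| 0 points | 3.0% | 2.7% |
| 5 points | 12.7% | 9.2% |
| 10 points | 31.5% | 22.8% |
| 15 points | 54.8% | 42.4% |
| 20 points | 75.3% | 63.2% |

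As a check on the 10% column, the normal approximation for a 10-point shift has standard error √[(0.20 × 0.80 + 0.10 × 0.90)/52] = 0.0693. Then 0.10/0.0693 = 1.442, and Φ(1.442 − 1.960) = 0.302, close to the exact 31.5%.

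If timing raises both arms equally from 10%, by up to 20 points, the chance stays between 2.7% and 3.0%. Only a difference between arms does harm.

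**4. How seconds could become points.** Assume exponential time to hemostasis with 40% at 180 s, so the rate is −ln(0.60)/180 = 0.002838 per second. If w seconds of readying had counted on the clock, the HEMOBLAST rate would be 1 − exp[−0.002838 × (180 − w)]. That is 34.7% for w = 30 and 28.9% for w = 60, a loss of 5 and 11 points. Against the planned FLOSEAL rate of 10%, the exact chance of success is 0.96 with no loss, 0.88 at 34.7% and 0.71 at 28.9%.

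**The case against.** A reader might infer that waiting and readying time drops off the clock for HEMOBLAST but never for FLOSEAL. The documents do not support this. Section 6.4 has both devices on hand unopened, one start rule applies to both, and any wait before opening is off the clock in either arm. No section says that FLOSEAL must be opened early or how long it takes to prepare. The pause rule also takes some waiting off the clock, mainly for the device that needs preparation. It is only a partial offset: it covers interrupted preparation and not the time before opening, and it leaves a count without durations.

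The written sequence also helps the plan. The site must be visible to be graded before randomization, Table 7 already lists randomization last before 00:00, and silence about delay is not permission to delay. This narrows the room for an arm-dependent start but does not close it, since no readiness condition or limit is stated.

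Nor is it right that nothing would show in the data. Both bleeding grades are presented, so a change within the eligible range can be compared by arm. The grades show a change in severity, however, and not elapsed time. A stopwatch reading at application would give time since opening, and so would still miss the interval from randomization to opening.

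Finally, FLOSEAL preparation on the clock is the stated objective. That stands in full, and the point here does not dispute it.

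**Conclusion.** The point holds in a limited form. An arm-dependent choice of the opening moment is possible, not restricted by the text, and not recorded. It acts on the only success criterion. The documents do not show that such a choice would be made, and they do not allow its size to be derived.

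The figures rest on assumed shifts acting on HEMOBLAST alone. With a common true rate of 10%, a shift of 5 or 10 points raises the chance of declaring superiority from 3.0% to 12.7% or 31.5%. At a common 20%, it goes from 2.7% to 9.2% or 22.8%. A reader might also infer that the trial's result hangs on this. Under the plan's own rates it mostly does not: losing 5 or 11 points from a true 30-point effect leaves a success chance of 0.88 or 0.71. The weight of the point is that a smaller or absent effect could pass and could not be audited. The remedy is cheap, and it removes a post-allocation choice from the primary endpoint, so the change is worth making.

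**What to change.** - **Section 6.4.2 and Table 7:** require that site and team are declared ready before the allocation is revealed, and that the package is opened directly afterwards, in both arms.
- **Section 6.4.5 and the Intraoperative CRF:** add the clock time of package opening beside the time of randomization.
- **Section 11:** report the randomization-to-opening interval by arm.

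A supportive analysis limited to subjects opened within a short interval is not advised. It would select on a choice made after randomization by a team that knows the arm, and so could bring in the bias it is meant to probe.

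Cost: protocol wording, one CRF field, one table, and slightly tighter sequencing in the operating room. Endpoint, intended inclusion of preparation time and sample size stay as they are. If no difference in timing occurs, the table will show it and support the sponsor's claim.

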## 6.4.3 Bleeding Severity and Hemostasis Evaluations

Bleeding severity and hemostasis will be assessed using the SBSS / SPOT GRADE™ at each time point.

A SPOT GRADETM score of 0 is equivalent to hemostasis. All other SPOT GRADETM scores are considered failure of hemostasis. See below in Table 6.

SBSS Score	0	1	2	3	4	5
Verbal Descriptor	None	Minimal	Mild	Moderate	Severe; not immediately life- threatening	Extreme; immediately life- threatening
Visual Descriptor	Dry	Oozing	Pooling	Flowing	Streaming	Gushing
Expected Intervention(s)	None	Manual pressure, cautery, adjuvant hemostat(s)	Manual pressure, cautery, suture, adjuvant hemostat(s)	Manual pressure, cautery, suture, adjuvant hemostat(s)	Manual pressure, cautery, suture, staples, tissue repair	Manual pressure, cautery, suture, staples, tissue repair
Maximum Expected ACS-ATLS Shock Risk Class	1	1	1	2	3	4
Hemostasis	Yes	No	No	No	No	No

#### Table 6. Bleeding Severity and Hemostasis

In any case where hemostasis is initially achieved but bleeding recurs prior to subject closure, the event will be documented.

## 6.4.4 Other Bleeding Sites

For bleeding sites other than the TBS, the Investigator may use any means necessary to control bleeding, including either the test or control hemostat. No study data will be collected for other bleeding sites.

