## 6.4 Intraoperative Procedures and Evaluations

All subjects will undergo the same intraoperative study evaluations. Intraoperative is defined as the time interval from when the subject enters the surgical suite until the subject exits the surgical suite.

Subjects undergoing the non-emergent cardiothoracic surgeries are eligible for enrollment into the clinical study. The Investigator will perform the surgery per his or her standard procedures, including conventional methods of hemostasis where practical (pressure, ligature, cautery, etc.).

Both test and control devices (not opened or prepared) should be available at the start of each procedure.

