## 7.2 Adverse Event Documentation

Only Adverse Events (AEs) possibly, probably, or definitely related to the hemostatic device (using the definitions below) will be recorded as part of this clinical study. AEs not related to the hemostatic device (the AE is due to the underlying disease state or is due to concomitant medications or therapy not related to the use of the hemostatic device) will not be recorded as part of this clinical study.

AEs will be documented by the Investigator on the appropriate source document(s) at the study site and also on the Adverse Event CRF. Adverse events are to be recorded and dated according to when they are first observed. The subsequent treatment(s) should also be documented. The following will be recorded on the Adverse Event CRF:

- Accepted medical term for the AE;
- Description of the event;
- Date of onset;
- Date of resolution, if applicable;
- Outcome;
- Treatment(s)/action(s) taken;
- Severity;
- Relationship to the hemostatic device; and
- Determination of reportability (see Reporting Section below).

The severity of the event will be determined by the Investigator using the following definitions:

- Mild: the symptoms are transient, barely perceptible by the subject and do not hinder normal activity; no treatment is usually prescribed to reduce these symptoms;
- Moderate: the symptoms are sufficiently severe to provoke discomfort in the subject and sufficiently uncomfortable to prevent normal activity; a treatment may be required; or
- Severe: the symptoms considerably modify the normal course of the subject's activities or are disabling or are life-threatening; the treatment studied should be suspended; a treatment for the symptoms is prescribed.

The relationship to the hemostatic device will be determined by the Investigator using the following definitions:

- Possibly related: the AE has a reasonable temporal relationship to the use of the hemostatic device but alternative etiology is equally or more likely compared to the potential relationship to the use of the hemostatic device;
- Probably related: the AE has a strong temporal relationship to the use of the hemostatic device and alternative etiology is less likely compared to the potential relationship to the use of the hemostatic device; or

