## **11.2.1** Analysis Populations

Safety analyses will be performed on the Full Analysis Population, defined as all subjects who were randomized into the study and received study intervention. Efficacy analyses will be conducted on the time to hemostasis (TTH) Analysis Population, defined as all subjects who were randomized, received study intervention, and had a TTH assessment recorded regardless of whether the measurement was censored (defined as the use of an additional hemostatic product or surgical rescue prior to the end of observation time, or failing to achieve and maintain complete hemostasis prior to the end of observation time). Data summaries will be based on the intervention received, regardless of which intervention was randomly assigned.

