## 11.3.2 Analysis of Safety Outcomes

11.3.2.1 Analysis Population

Safety analyses will be conducted on the Safety Analysis Population, defined as all subjects who were randomized into the study and received study intervention.

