11.3.2.2 Methods of Analysis

Summaries of the number and percent of subjects with at least one device-related AE will be provided. Comparisons of the proportion of subjects experiencing SADEs and UADEs will be made between treatment arms.

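### Use of either study hemostat at non-target sites is allowed but not recorded, so device-related adverse events in dual-exposed subjects cannot be reliably attributed to a device

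*Combined protocol and SAP*

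**What the plan says.** At bleeding sites other than the target bleeding site (TBS), Section 6.4.4 provides that "the Investigator may use any means necessary to control bleeding, including either the test or control hemostat". The next sentence reads: "No study data will be collected for other bleeding sites". Cross-use is practical in every case, because Section 6.4 requires that "Both test and control devices (not opened or prepared) should be available at the start of each procedure".

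The data items match that rule. The Intraoperative CRF list in Section 6.4.5 has no entry for hemostat use away from the TBS, and it places the device lot or batch number under randomization, next to treatment arm. Section 7.2 limits capture as follows: "Only Adverse Events (AEs) possibly, probably, or definitely related to the hemostatic device (using the definitions below) will be recorded". The Adverse Event CRF items listed there include one relationship field, with nothing on which hemostat or which site is suspected.

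On the analysis side, Section 11.2.1 states: "Data summaries will be based on the intervention received, regardless of which intervention was randomly assigned". Section 11.3.2.1 states: "Safety analyses will be conducted on the Safety Analysis Population, defined as all subjects who were randomized into the study and received study intervention". Section 11.1.3 summarises device malfunctions, device-related AEs, SADEs and UADEs by treatment group, and Section 11.3.2.2 adds: "Comparisons of the proportion of subjects experiencing SADEs and UADEs will be made between treatment arms".

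**The concern.** The planned safety analysis needs an exposure that the protocol says will not be collected. A subject randomised to FLOSEAL may receive HEMOBLAST elsewhere in the same operation, and the reverse, and nothing on the listed forms will show it. No section limits the intervention received to the device applied to the TBS or says how to classify a subject who had both.

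This matters because several risks listed in Section 12.2 need not arise at the TBS: allergy or anaphylaxis, thromboembolism, viral transmission, and blockage of bypass or cell-saver systems. The same section warns that hypersensitivity reactions may become more frequent with repeated HEMOBLAST applications. Unrecorded non-target use is therefore unrecorded exposure to a risk factor that the protocol itself names, including within the HEMOBLAST arm.

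At stake is the reading of the device safety tables. An event in a dual-exposed subject may be set against the wrong product, and no analysis done afterwards could find or remove those subjects from the planned data.

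**Working it through.** **Setting the sections side by side**

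- Is non-target exposure permitted? Yes, to either product in either arm (6.4.4), with both in the room (6.4).
- Is it recorded? No (6.4.4), and no item in 6.4.5 or 7.2 would capture it indirectly.
- Is the suspected device recorded for an event? No item is listed (7.2).
- Is randomised arm recorded? Yes (6.4.5). Events can be counted by arm.
- Is the grouping rule defined for a dual-exposed subject? No (11.2.1, 11.3.2.1).

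Counting by arm survives. Attribution to a device does not, in an unknown set of subjects.

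**Plan figures**

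The documents give no figure for cross-use or for adverse event rates, so there is no planned safety figure to reproduce. The sample size is not in dispute. For 0.40 versus 0.10 at one-sided 0.025 and 90% power, the pooled normal formula with continuity correction gives 49 per arm. Allowing for 5% attrition, 98/0.95 = 103.2, which rounds up to 104, or 52 per arm. Nothing below changes it.

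**Size of the effect, under assumed inputs**

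Let rH and rF be the risks of a device-caused event for HEMOBLAST and FLOSEAL. Let cH and cF be the shares of the HEMOBLAST and FLOSEAL arms that also receive the other device. Assume the two risks act independently and that non-target exposure carries the full risk. None of these values is in the documents.

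- HEMOBLAST arm rate = 1 − (1 − rH)(1 − cH·rF)
- FLOSEAL arm rate = 1 − (1 − rF)(1 − cF·rH)
- Difference = rH(1 − cF) − rF(1 − cH) − rH·rF(cH − cF)

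*Equal cross-use.* With cH = cF = c the last term vanishes and the difference is (1 − c)(rH − rF). In percentage points:

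| c (assumed) | 5% vs 1% | 10% vs 2% |
|---|---|---|
| 0 | 4.0 | 8.0 |
| 10% | 3.6 | 7.2 |
| 25% | 3.0 | 6.0 |
| 50% | 2.0 | 4.0 |
| 100% | 0 | 0 |

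For 5% vs 1% at c = 50%, the arm rates are 1 − 0.95 × 0.995 = 5.475% and 1 − 0.99 × 0.975 = 3.475%. In 52 subjects per arm that is 2.85 and 1.81 expected events, against 2.60 and 0.52 without cross-use.

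*Unequal cross-use.* Take rH = rF = 5%, so there is no true difference, with cH = 10% and cF = 50%. The arm rates are 1 − 0.95 × 0.995 = 5.475% and 1 − 0.95 × 0.975 = 7.375%. A spurious difference of 1.9 points appears, to the disadvantage of the arm with more cross-use. Reversing the two shares reverses the sign.

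*Granularity.* One misattributed event in an arm of 52 is 1/52 = 1.9 points, so a single case is as large as that spurious difference.

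**The case against.** The strongest counter-argument has four parts.

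1. *Arm is known for every subject.* Treatment arm is on the Intraoperative CRF, and Section 11.3.2.2 compares arms. A reader might infer from Section 6.4.4 that events cannot be assigned to an arm at all. The documents do not support that, and this part stands in full. What is blurred is the device responsible, and only in dual-exposed subjects.

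2. *Intervention received has a natural meaning.* Section 6.4.1 has one TBS per subject assessed for study purposes, and Section 6.4.2 applies the assigned hemostat to it. Reading the phrase as the device applied to the TBS is sensible, but the text does not say so. That reading would settle the grouping and still leave cross-exposure unmeasured.

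3. *Source records may help.* Section 8.2 lists operative reports among possible sources, and the adverse event form takes a description, so exposure for a rare SADE might be traced. That could help with single cases. It does not supply the number exposed to both devices.

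4. *The stakes are limited.* Safety is not a stated objective or endpoint (Sections 5.1.1 to 5.4), no test is named for it, and subjects leave the study after the intraoperative visit. Many delayed events would go unobserved in either arm, and some listed risks, such as nerve compression, are local and may be traceable to a site. This stands and keeps the point modest. With few events, though, each misattribution weighs more.

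A reader might also infer that the efficacy result is contaminated. Hemostasis is scored only at the TBS, where the assigned device is applied. Section 11.2.1 treats use of an additional hemostatic product before the end of observation as censoring, and Section 11.2.2 counts values censored before the reading as failures. The censoring rule most naturally refers to the TBS, though it does not say so. An effect of product used near the TBS on the reading would be speculation.

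**Conclusion.** The point holds as a gap in safety data and analysis. Followed as written, the plan yields safety summaries by intervention received and a between-arm SADE and UADE comparison with a cross-exposure that can be neither measured nor adjusted for, because dual-exposed subjects are not identified and the suspected device is not recorded.

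The bias has no known size or direction. The (1 − c) shrinkage might be read as a general rule, but it holds only when cross-use is equal in both arms, and nothing in the documents supports or excludes that. Unequal use can create a difference where none exists. All numerical illustrations rest on assumed risks and shares, independence, and full risk from non-target exposure.

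The primary 3-minute comparison at the TBS is not materially affected, and neither the sample size nor the primary test needs to change. The change is worth making because it is cheap and the information cannot be recovered from the planned forms.

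**What to change.** Four changes, to be made before enrolment because the planned CRFs will not hold the data:

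- **Section 6.4.4, last sentence (with matching items in Section 6.4.5).** Replace with: *No efficacy data will be collected for other sites, but the CRF will record whether HEMOBLAST and/or FLOSEAL was used at any non-target site, and whether before the 5-minute reading.*
- **Section 7.2, Adverse Event CRF.** Add the suspected device (HEMOBLAST, FLOSEAL, both, or cannot be determined) and the suspected site (TBS, other, or not site-specific).
- **Section 11.2.1.** Define intervention received as the device applied to the TBS. This keeps the as-received convention and gives every treated subject one group.
- **Section 11.3.2.2.** Add a safety table that separates subjects exposed to one device from those exposed to both.

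The cost is a few CRF fields and one extra table. Patient care is unchanged, including the investigator's freedom at non-target sites. The table is descriptive: non-target use is not randomised, so a contrast between single- and dual-exposed subjects should not be read causally.
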